8.4.2 Handling of missing data

In primary analysis, outcome values will not be imputed. Further sensitivity analysis for the impact of potential missing data will be conducted following study completion using multiple imputation analysis.

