8.0 SAMPLE SIZE AND STATISTICAL PLAN

This is a single site, randomized, open-label trial comparing the effect of the brachytherapy specific video versus verbal standard consent in patients receiving gynecologic brachytherapy(N=80).

8.1

Study Design/Study Endpoints

In this open-label study design, eligible participants will be randomized using a simple 1:1 schedule to either brachytherapy verbal standard consent (Arm A), or the brachytherapy specific video (Arm B), based on chronological arrival in clinic. There will be three time points for the collection: after the standard verbal consent process at baseline, following the standard vs video brachytherapy education, and prior to the last brachytherapy procedure.

Primary outcomes will be judged from a Likert-scale questionnaire. Patients will be given a Likert-scale questionnaire to assess their satisfaction with the information provided about the brachytherapy procedure which was adapted from a previously-published, validated instrument, and was published by our brachytherapy group². We will also assess the reduction in procedure-related anxiety based on the video intervention using the validated National Comprehensive Cancer Network patient anxiety screening tool.

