8.2 Power and Sample Size Determination

Study Power: Estimates of study power are based on two-sample t-tests comparing outcomes between patients provided with brachytherapy informed video versus standard of care verbal consent. We based power estimates on a sample-size of 80 participants (40 pts with brachytherapy informed video and 40 with standard of care verbal consent). We used PASS 14 (NCSS Statistical Software). Assuming a two-sided test with alpha=0.05, we have 80% power to detect a 3.2 mean difference between armse.g., 57.5 mean score in patients with brachytherapy informed video versus a 54.3 mean score in patients with standard of care verbal consent, assuming SD of 2.7 and 6.4, respectively.

Accrual will be based on chronological arrival in clinic. Approximately 250 brachytherapy gynecologic procedures are performed at UCSD and collaborating sites annually. Accrual of 80 participants could occur over 2 years. Annual target accrual will be 40 participants per year.

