8.3 Evaluable Subjects and Subject Replacement

The intent-to-treat (ITT) data set will include all eligible individuals who are randomized. The per-protocol (PP) data set will include all patients having completed all three data collection time points as assessed by the brachytherapy-specific survey, and NCCN distress score.

Data will not be analyzed until we have reached target accrual. Given the short duration of the intervention to the end of treatment we do not anticipate any issues with the number of evaluable subjects. Should a subject withdraw an additional subject would be randomized and enrolled. A slight imbalance is accepted.

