8.4 Efficacy Analysis

8.4.1 Analysis of Primary Endpoint

The primary analysis will be based on the Intention-to-Treat population, defined as all individuals who were randomized to arm A or arm B. A Likert-scale questionnaire is used to calculate satisfaction score.

Using the brachytherapy specific questionnaire, we will examine three patient reported time points for impact: baseline, after the consent process, and prior to the last brachytherapy procedure. For primary endpoint, we will use a two-sample t-test to compare differences of satisfaction scores at two time points (baseline and following consent process) between groups. We do not anticipate any possible confounders, if any we will include it in the secondary analysis.

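### The primary analysis is labelled ITT but uses only randomised patients with both surveys; loss that relates to score differently by arm could bias it, probably modestly, and no specified analysis tests for that.

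*Combined protocol and SAP*

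**What the plan says.** All references are to the combined protocol and SAP.

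- Section 8.4.1: "The primary analysis will be based on the Intention-to-Treat population", defined there as everyone randomised to either arm. The test is a two-sample t-test on the difference between the baseline and post-consent satisfaction scores, without covariates. Section 5.1 also defines the outcome as this change.
- Section 8.4.2: "In primary analysis, outcome values will not be imputed". Multiple imputation is named as a later sensitivity analysis. No imputation model, variables, missingness assumption or number of imputations is given.
- Section 8.3: the ITT set is limited to eligible randomised patients, which differs from section 8.4.1. On withdrawals: "Should a subject withdraw an additional subject would be randomized and enrolled". The section expects no difficulty with evaluable numbers because the study period is short.
- Section 8.4.3: a secondary repeated-measures model of the same score, with baseline score, age and stage as covariates.
- Section 8.2: "we have 80% power to detect a 3.2 mean difference", "assuming SD of 2.7 and 6.4, respectively" for the video and standard arms, with 40 patients per arm and no allowance for loss.

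**The concern.** A change score exists only when both surveys exist. Without imputation, the t-test is a complete-case analysis whatever the population is called. Its validity then rests on an assumption about loss that the plan does not state.

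The assumption is not trivial here. The trial is open-label (section 8.0), the outcome is self-reported satisfaction, and only Arm B is asked to log in and watch a video (sections 1.2 and 4.1). The reasons for not returning the second survey could therefore differ between arms. If dissatisfied patients were lost more often from Arm B, the video would look better than it is. If Arm B patients with low baseline scores were lost more often, it would look worse.

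The only analysis named as a missing-data check is the multiple imputation. In its standard form it assumes data are missing at random, so it would not show how the result changes if loss depends on the unseen score.

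**Working it through.** **1. The plan's own power figure.** Inputs from section 8.2: 40 per arm, difference 3.2, SDs 2.7 and 6.4, two-sided alpha 0.05.

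- SE = √(2.7²/40 + 6.4²/40) = √(0.182 + 1.024) = 1.098.
- Noncentrality = 3.2/1.098 = 2.91.
- Welch (unequal-variance) power is 81.6%, so the stated 80% is reproduced.

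With equal, unreplaced loss (rates assumed), Welch power would be 77.3% at 10% (36 per arm) and 74.8% at 15% (34 per arm). Enrolling extra patients protects against this loss of power.

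**2. When complete-case analysis is biased.** Within an arm, let q be the fraction lost and D the mean change of observed patients minus that of lost patients. The observed mean exceeds the full-arm mean by q × D. The treatment contrast (B minus A) is therefore off by

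q_B × D_B − q_A × D_A.

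Random loss has D = 0, so unequal loss rates alone do no harm. With loss in Arm B only, 15% and D = 3.2 give 0.15 × 3.2 = 0.48 points. With D = 6.4, the result is 0.96.

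**3. Simulation with no true effect.** 6,000 trials per scenario, 40 per arm, SD 4.91 (root mean square of 2.7 and 6.4), assumed baseline to post-consent correlation 0.5. At that correlation the change SD equals the score SD, since √(2(1 − 0.5)) = 1.

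| Loss pattern | Mean bias at 10% / 20% loss | Type I error |
|---|---|---|
| Random, both arms | −0.01 / −0.02 | 5.1% / 4.8% |
| Random, Arm B only | −0.01 / +0.02 | 5.2% / 4.9% |
| Low post-consent scores lost, both arms alike | −0.01 / 0.00 | 4.8% / 5.7% |
| Low post-consent scores lost in B, random in A | +0.23 / +0.46 | 5.6% / 7.0% |
| Low baseline scores lost in B, random in A | −0.24 / −0.47 | 5.5% / 6.5% |

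**4. Simulation with a true effect of 3.2.** 5,000 trials per scenario, 40 per arm. Assumed: SD 5, correlation 0.5, loss in Arm B only, following a logistic model with slope 1 to 2 per SD.

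| Loss in Arm B | Change t-test | Baseline-adjusted |
|---|---|---|
| Baseline-related, 8% | 2.88 to 3.03 | 3.18 to 3.21 |
| Baseline-related, 15% | 2.69 to 2.86 | 3.18 to 3.21 |
| Outcome-related, 8% | 3.37 to 3.48 | 3.46 to 3.65 |
| Outcome-related, 15% | 3.53 to 3.72 | 3.69 to 3.98 |

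Subtracting 3.2, t-test bias is −0.17 to −0.51 for baseline-related loss and +0.17 to +0.52 for outcome-related loss. Adjustment removes the first. Under the second it is worse than the t-test, with bias of +0.26 to +0.78.

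**5. Using the plan's unequal SDs.** With 2.7 in Arm B and 6.4 in Arm A (assumed to hold at baseline too), t-test bias from outcome-related Arm B loss was about 0.08 at 8% and 0.18 at 15%. The same loss model with SD 5 gave 0.19 and 0.32.

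**6. Precision.** With no loss, SD 5 and correlation 0.5, the SE of the change contrast is 5 × √(2/40) = 1.12. The baseline-adjusted SE is 5 × √(1 − 0.5²) × √(2/40) = 0.97. Simulation gave 1.11 and 0.97.

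**The case against.** The strongest counter-argument is that nothing in the documents points to material or differential loss. The primary interval closes before the first procedure, and section 8.3 expects few problems. The loss rates, the restriction to Arm B, the SD of 5 and the correlation are all assumptions, and the plan's own Arm B SD shrinks the bias. This stands: the concern is a risk of unknown size, not a demonstrated bias.

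Three stronger readings are tempting, and the documents do not support them.

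- A reader might infer that any loss linked to arm biases the result. Random loss in one arm gave no bias. Nor did the same outcome-related loss in both arms, although that check used equal SDs; with unequal SDs, D can differ between arms even under one loss mechanism.
- A reader might infer that replacing withdrawn patients creates bias or conceals loss. Section 8.3 randomises an additional patient and does not remove the withdrawn one from the ITT set. This restores numbers without recovering the lost outcomes, and nothing prevents reporting withdrawals.
- A reader might infer that multiple imputation is the only other look at the data. The section 8.4.3 model is a second analysis of the same score, valid under missing at random, though it is not designated as a missing-data check.

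It is also fair to object that changing the primary analysis is not a complete cure. With baseline as a covariate, the section 8.4.3 model cannot use patients with no post-baseline score, and it is more biased than the t-test when dissatisfied Arm B patients leave. Both points stand and limit what the change can claim.

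**Conclusion.** The point holds in a limited form. The label and the analysis do not match: the primary test uses randomised patients with both surveys, under an unstated assumption about loss. Bias arises only if loss displaces the observed mean by different amounts in the two arms. At an assumed 8% to 15% loss in Arm B only, it is about 0.1 to 0.5 points, or roughly 3% to 16% of the 3.2-point target (0.1/3.2 and 0.5/3.2), upwards or downwards according to the type of loss. Heavier or more selective loss would do more. The documents give no loss rate, so the actual size is unknown and probably modest.

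The documents do not support saying that the primary result will be biased, or that replacement is at fault. They do show that the imputation is unspecified and that no analysis is committed to testing outcome-related loss. This should be corrected, but it does not invalidate the design.

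**What to change.** 1. **Section 8.4.1.** Take the primary Arm B minus Arm A contrast at the post-consent time point from the baseline-adjusted repeated-measures model of section 8.4.3. Include every randomised patient with a baseline and at least one post-baseline score, and state the missing-at-random assumption. This improves precision, removes bias from baseline-related loss, and brings in patients who miss the second survey but complete the third. State also that it does not recover patients with no post-baseline score and is somewhat more biased than the change t-test under outcome-related loss in one arm. Keep the t-test as a supportive analysis, described as using patients with both scores.
2. **Section 8.4.2.** Specify the multiple imputation: by arm, with baseline score, age, stage and the later score, and a stated number of imputations. Add a delta-adjusted (tipping-point) version that shifts imputed Arm B scores over a range stated in advance. The model in item 1 should not be adopted without this check.
3. **Sections 8.3 and 8.4.1.** Use one ITT definition, all randomised patients. State that withdrawn patients remain in it alongside any additional patients, and report loss and its reasons by arm.

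The cost is SAP wording and modest programming, since the model and the imputation are already planned. The primary analysis becomes slightly less simple than a t-test.

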8.4.3 Analysis of Secondary Endpoints

Satisfactory scores at three time points will be analyzed using a mixed effect model for repeated measures (MMRM) to assess satisfactory scores trajectories between two arms. The MMRM model will include terms for time, consent arm, baseline score, arm-by-time interaction, baseline score by time interaction, plus covariates that include age, stage. Time will be treated as categorical.

If values of last two time points are similar, analysis of covariance model (ANCOVA) will be used to model the change in satisfactory scores. The mean of the last two time points will be calculated. That is, the after consent score (mean values) will be regressed upon baseline score and consent arms. Patient treatment-related anxiety between groups, defined as NCCN distress score, are also collected at three time points and will be analyzed using the same strategy.

9 STUDY MANAGEMENT

9.1 Conflict of Interest

Any investigator who has a conflict of interest with this study (patent ownership, royalties, or financial gain greater than the minimum allowable by their institution, etc.) must have the conflict reviewed according to UCSD conflict of interest policy.

9.2 Institutional Review Board (IRB) Approval and Consent

The IRB should approve the consent form and protocol prior to any study-related activities. It is expected that the IRB will have the proper representation and function in accordance with federally mandated regulations.

In obtaining and documenting informed consent, the investigator should comply with the applicable regulatory requirement(s), and should adhere to Good Clinical Practice (GCP) and to ethical principles that have their origin in the Declaration of Helsinki.

Before recruitment and enrollment onto this study, the patient will be given a full explanation of the study and will be given the opportunity to review the consent form. Each consent form must include all the relevant elements currently required by the FDA Regulations and local or state regulations. Once this essential information has been provided to the patient and the investigator is assured that the patient understands the implications of participating in the study, the patient will be asked to give consent to participate in the study by signing an IRB-approved consent form.

Prior to a patient's participation in the trial, the written informed consent form should be signed and personally dated by the patient and by the person who conducted the informed consent discussion.

Any recruitment materials developed for this project will be submitted for IRB review prior to their use.

9.3 Subject Data Protection

In accordance with the Health Information Portability and Accountability Act (HIPAA), subjects who have provided written informed consent must also sign a subject authorization to release medical information to the study Sponsor and allow a regulatory authority, or Institutional Review Board access to subject's medical information relevant to the study.

9.4 Data and Safety Monitoring/Auditing

In addition to adverse event monitoring and clinical oversight by [name], UCSD

principal investigator and co-investigators, quality assurance of the study will be performed by the UCSD Moores Cancer Center Clinical Trials Office internal monitor. Monitoring intervals will be dependent upon the number of patients enrolled and the complexity of the study.

This study will also use the UCSD Moores Cancer Center Data Safety and Monitoring Board (DSMB) to provide oversight in the event that this treatment approach leads to unforeseen toxicities. Data from this study will be reported when<minimum annually, frequency related to risk; can ask for recommendations from DSMB> and will include:

- 1) the protocol title, IRB protocol number, and the activation date of the study.
- 2) the number of patients enrolled to date
- 3) the dates of patient enrollment
- 4) a summary of all adverse events regardless of grade and attribution
- 5) a response evaluation for evaluable patients when available
- 6) a summary of any recent literature that may affect the ethics of the study.

9.5 Adherence to the Protocol

Except for an emergency situation in which proper care for the protection, safety, and well-being of the study patient requires alternative treatment, investigators are required to conduct their research according to the plans reviewed and approved by the IRB.

9.6 Amendments to the Protocol

Should amendments to the protocol be required, the amendments will be originated and documented by the Study Chair. It should also be noted that when an amendment to the protocol substantially alters the study design or the potential risk to the patient, a revised consent form might be required.

The written amendment, and if required the amended consent form, must be sent to the IRB for approval prior to implementation.

9.7 Record Retention

Study documentation includes all Case Report Forms, data correction forms or queries, source documents, Sponsor-Investigator correspondence, monitoring logs/letters, and regulatory documents (e.g., protocol and amendments, IRB correspondence and approval, signed patient consent forms).

Source documents include all recordings of observations or notations of clinical activities and all reports and records necessary for the evaluation and reconstruction of the clinical research study.

Government agency regulations and directives require that the study investigator must retain all study documentation pertaining to the conduct of a clinical trial. In the case of a study with a drug seeking regulatory approval and marketing, these documents shall be retained for at least two years after the last approval of marketing application in an International Conference on Harmonization (ICH) region. In all other cases, study documents should be kept on file until three years after the completion and final study report of this investigational study.

9.8 Obligations of Investigators

The Principal Investigator is responsible for the conduct of the clinical trial at the site in accordance with Title 21 of the Code of Federal Regulations and/or the Declaration of Helsinki.

The Principal Investigator is responsible for personally overseeing the treatment of all study patients. The Principal Investigator must assure that all study site personnel, including sub-investigators and other study staff members, adhere to the study protocol and all FDA/GCP/NCI regulations and guidelines regarding clinical trials both during and after study completion.

The Principal Investigator at each institution or site will be responsible for assuring that all the required data will be collected and entered onto the Case Report Forms. Periodically, monitoring visits will be conducted and the Principal Investigator will provide access to his/her original records to permit verification of proper entry of data. At the completion of the study, all case report forms will be reviewed by the Principal Investigator and will require his/her final signature to verify the accuracy of the data.

11 APPENDICES

Appendix A. Performance Status

ECOG Performance Status Scale		Karnofsky Performance Scale	
Grade	Descriptions	Percent	Description
0	Normal activity. Fully active, able to carry on all pre-disease performance without restriction.	100	Normal, no complaints, no evidence of disease
		90	Able to carry on normal activity; minor signs or symptoms of disease.
1	Symptoms, but ambulatory. Restricted in physically strenuous activity, but ambulatory and able to carry out work of a light or sedentary nature (e.g., light housework, office work).	80	Normal activity with effort; some signs or symptoms of disease.
		70	Cares for self, unable to carry on normal activity or to do active work
2	In bed < 50% of the time. Ambulatory and capable of all self-care, but unable to carry out any work activities. Up and about more than 50% of waking hours.	60	Requires occasional assistance, but is able to care for most of his/her needs.
		50	Requires considerable assistance and frequent medical care
3	In bed > 50% of the time. Capable of only limited self-care, confined to bed or chair more than 50% of waking hours	40	Disabled, requires special care and assistance.
		30	Severely disabled, hospitalization indicated. Death not imminent
4	100% bedridden. Completely disabled. Cannot carry on any self-care. Totally confined to bed or chair	20	Very sick, hospitalization indicated. Death not imminent.
		10	Moribund, fatal processes progressing rapidly
5	Dead.	0	Dead.

Appendix B. NCCN Distress Tool

Instructions: Below, circle the number (0-10) that best describes how much distress or anxiety you have been experiencing as it relates to your planned brachytherapy procedure.
 
Extreme distress or anxiety
  
No distress or anxiety
	
Instructions: Below, circle the number (0-5) that best describes how much the following problems have been affecting you.
 

	None at All	Rarely Ever	Not Very Much	Some	Often	Very Much	

Depression	0	1	2	3	4	5	

Fear	0	1	2	3	4	5	

Nervousness	0	1	2	3	4	5	

Sadness	0	1	2	3	4	5	

Worry	0	1	2	3	4	5	

Loss of interest in activities	0	1	2	3	4	5	

Changes in urination	0	1	2	3	4	5	

Constipation	0	1	2	3	4	5	

Diarrhea	0	1	2	3	4	5	

Nausea	0	1	2	3	4	5	

Getting around	0	1	2	3	4	5	

Indigestion	0	1	2	3	4	5	

Pain	0	1	2	3	4	5	

		None at All	Rarely Ever	Not Very Much	Some	Often	Very Much	Depression	0	1	2	3	4	5	Fear	0	1	2	3	4	5	Nervousness	0	1	2	3	4	5	Sadness	0	1	2	3	4	5	Worry	0	1	2	3	4	5	Loss of interest in activities	0	1	2	3	4	5	Changes in urination	0	1	2	3	4	5	Constipation	0	1	2	3	4	5	Diarrhea	0	1	2	3	4	5	Nausea	0	1	2	3	4	5	Getting around	0	1	2	3	4	5	Indigestion	0	1	2	3	4	5	Pain	0	1	2	3	4	5
	None at All	Rarely Ever	Not Very Much	Some	Often	Very Much																																																																																													
Depression	0	1	2	3	4	5																																																																																													
Fear	0	1	2	3	4	5																																																																																													
Nervousness	0	1	2	3	4	5																																																																																													
Sadness	0	1	2	3	4	5																																																																																													
Worry	0	1	2	3	4	5																																																																																													
Loss of interest in activities	0	1	2	3	4	5																																																																																													
Changes in urination	0	1	2	3	4	5																																																																																													
Constipation	0	1	2	3	4	5																																																																																													
Diarrhea	0	1	2	3	4	5																																																																																													
Nausea	0	1	2	3	4	5																																																																																													
Getting around	0	1	2	3	4	5																																																																																													
Indigestion	0	1	2	3	4	5																																																																																													
Pain	0	1	2	3	4	5																																																																																													

